The following information will be obtained from human subjects: Name, age, contact information, date of stroke, time since stroke, ethnicity, brief post-stroke medical history. Data that will be recorded from human subjects will include rating-scale assessments of upper extremity motor ability, kinematic motion analysis of upper extremity movement, measurements of upper extremity strength, and upper extremity electromyography. Identifiable information will be stored in password-protected files on a secure MUSC network (MUSC patients) or on the VA-network (VA patients). All data will be coded with a unique study identifier. The only people having access to this identifiable information will be [name] and her research study staff (named on this protocol). No other person will have access to PHI for study participants. All data will be de-identified with all personal identifiers removed for data analysis. That is, the PHI will be stripped of its identifiers for data analysis. Data analysis will incorporate only aggregate data that does not contain any participant-specific identifiers. There will be no way to link the data being analyzed back to the individual. Hard copy data will be coded by unique study identifier and stored in a locked file cabinet which is located along the east wall of the secured office of the principal investigator which is located in room #307 of the College of Health Professions Research Building at [name]. This space is designated as a VA research space in a VA approved memorandum of understanding. Once the study is completed data (described below) will be de-identified. Potential participants will be identified through recruiting mechanisms described above associated with the MUSC Stroke Center and VA PM&R service. The PI and/or study coordinator for the present study will provide the MUSC Stroke Center and VA PM&R service with inclusion/exclusion criteria. Personnel associated with either of these places will then provide our contact information to participants. Participants will then initiate contact with either the PI or Study Coordinator of the present study. If potential participants meet inclusion criteria they will be asked by the study coordinator if they would like to participate in the current study. If they do wish to participate, they will be scheduled for a time to obtain written informed consent to participate in the study.

c. Potential Risks

Potential discomforts or risks for participation in this study are minimal. This is a prospective study with parallel arm design. Subjects will undergo 4 evaluation sessions (Pre-treatment, Mid-Treatment, Post-Treatment, 30 day Follow Up). Assessments will consist of (1) clinical rating scale assessments and (2) motion and EMG analysis. During both types of assessment sessions, subjects will be seated comfortably. They will be asked to perform UE movements commonly performed in everyday life (e.g., lift arm to eye level while keeping elbow straight, pick up a soda can). Sensors for motion and EMG analysis are attached to the participants' skin. There may be a temporary skin reaction to the adhesive used to secure the motion analysis markers or EMG sensors to the skin. To minimize this, the skin will be cleaned before and after the markers or sensors are placed on the skin and hypoallergenic gel and tape will be used on the skin. A skin reaction is a rare occurrence and resolves within 1-2 days. All participants will be asked if they have had any previous experience of allergic reaction to specific gel or tape types. If they answer yes, then we will avoid placing markers or sensors directly on the skin. Instead we will wrap the limb in non-sticky "pre-wrap" and attach motion sensors to it. Pre-wrap is a soft wrap often used under casts or braces.

Subjects will be randomized to two stroke rehabilitation treatment groups; "targeted" vs. "non-targeted" and will engage in 12 rehabilitation treatment sessions. The only difference between the treatments is that the "targeted" group will receive specific instructions from the therapist regarding the participants' quality of movement during rehabilitation treatment (e.g., straighten elbow, sit tall). During rehabilitation treatment, participants will be asked to practice using the arm most affected by stroke. They will perform 200 movement repetitions during rehabilitation treatment. The will include reaching, grasping and lifting common everyday objects. Participants may be seated or standing for these activities. While standing, all participants will be closely guarded by study personnel to monitor and maintain balance. In previous studies, 200 repetitions of reaching movement using the hemiparetic UE required approximately 2 hours with no reports of increased pain or fatigue although subjects will be offered a rest break after every set of 10 movements.

There is a very low risk of a seizure after TMS (7 reported cases in almost 7000 studies). The risk of seizure induction by this protocol has been thoroughly assessed and our TMS parameters will be well within published safety guidelines. Of these 7 cases, none has required external intervention in the form of medications to stop the seizure, and no patient has had any post-seizure sequelae, nor have they developed recurrent seizures. To minimize risk, we only use single pulse TMS, as the majority of adverse events have occurred after repetitive TMS and we will follow published safety guidelines. Anyone with a history of seizure will not be allowed to participate in this portion of the study.

Headaches are the most common complaint from patients following treatment with TMS. In one study conducted by George and Belmaker (2007)⁷⁸, 19% of healthy subjects reported having headaches after treatment with TMS. However, 17% receiving sham TMS also reported headaches after the session. These are generally self-limiting and respond to common analgesics like aspirin.

Potential Risks of MRI: MRI is considered minimal risk.

1. Although the risks from magnetic resonance imaging (MRI) are low, it is critical that you do not have **metal** in the skull, metal implants, a cardiac or brain pacemaker, or old metal fragments in the eye or retina. If you/your child have a question about metal in your body, inform the researchers and they will determine whether it is safe in a MRI scan.
2. Some discomfort may occur from having **to remain still** while you are in the MRI scanner. During the scanning you will be given an emergency ball to squeeze at any time you are feeling discomfort and desire to be pulled out of the scanner.
3. The MRI scanner is noisy, and there is a risk of **hearing damage** if you do not wear earplugs. As stated above, to eliminate this risk, you will be given earplugs to wear during each scan.
4. Although the MRI scanner is open on both ends, some people become anxious or claustrophobic when entering the MRI scanner due to the **feeling of being enclosed**. If this has happened to you in the past, inform the study personnel, as you/your child may be ineligible for the study. The researchers will work with you to keep this from happening by allowing you to view relaxing pictures on a screen prior to the start of the research procedure (until any anxiety has passed). Also, the researchers can talk with you during the procedure through a microphone in the scanner to reduce your concern.
5. If you are female and of child-bearing potential, you must have a **pregnancy** test performed prior to the scanning procedures. This test must be negative for you to participate in the study. If pregnant you will not be eligible to continue in the study.
6. Unknown Risks: The experimental procedures may have unknown side effects. The researchers will let you know if they learn anything that might make you change your mind about participation

A licensed occupational or physical therapist will oversee all evaluation and treatment sessions. The therapist will monitor the participant for safety and offer rest breaks when he/she determines that the patient needs one.

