Sample size was calculated based on FMA-UE data obtained from our pilot study (see Preliminary Studies) to determine whether there is a statistical difference in people receiving targeted rehabilitation vs. a comparison non-targeted intervention in the present parallel arm design with 6 treatment groups. Specifically, we will test $H_0: \mu_{\text{targeted}} = \mu_{\text{non-targeted}}$, versus the two tailed alternative $H_a: \mu_{\text{targeted}} \neq \mu_{\text{non-targeted}}$. The pilot study demonstrated that the targeted (trunk restraint) group exhibited a post-training Rasch-derived FMA-UE person ability measure of 2.30 (± 1.00) logits, while the non-targeted intervention (mCIMT) group exhibited a post-training Rasch FMA-UE score of 1.42 (± 0.45) logits which yields a Cohen's d effect size of 1.13. With an alpha level = 0.05, for a two-tailed hypothesis test at a 90% power level, the sample size calculation specified that 18 individuals are needed in each group to answer the research hypothesis confidently. With 6 treatment groups,

Group data (not presented) suggested that participants demonstrated expected UE movement patterns prior to the intervention in that while attempting to reach forward they had difficulty extending the elbow while flexing the shoulder. Participants who underwent an intervention specifically aimed at altering this movement pattern demonstrated a statistically significant Pre to Post gain in voluntary elbow extension ranges of motion whereas those who underwent an intervention that was not aimed at altering the compensatory movement pattern showed very little gain in voluntary elbow extension. For example 4 out of 5 participants in the targeted treatment group showed increased elbow extension angular excursion, while 4 out

N=108. Based on the stroke rehabilitation literature we anticipate a 20% drop out rate and therefore will enroll **N=130** subjects.

Project Timeline:

	Jan	Feb	Mar	Apr	May	Jun	Jul	Aug	Sept	Oct	Nov	Dec
Yr1					Preparation and Recruitment					Enroll 20 patients		
Yr2								Enroll 48 patients				
Yr3								Enroll 40 patients				
Yr4				Complete follow-up tests					Data analysis and manuscript preparation			

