We will follow implementation of the therapy as per the published manual, online videos and available implementation guidelines. In addition, the PI recently attended an 8 hour workshop to develop competence in providing the therapy. We argue that Functional Upper Extremity Training⁷⁷ is not a "targeted" intervention according to our definition. That is, the approach does not specifically target a person-ability level because there will be no guidance from a measurement framework from which to choose appropriate tasks to ameliorate underlying specific deficits.

Specific to Aim 1: Compare the effects of targeted rehabilitation versus *non*-targeted rehabilitation on UE motor function.

Hypothesis: Targeted intervention will result in a greater pre- to post-intervention reduction of UE motor impairment when compared to *non*-targeted intervention.

Rationale: The Rasch-based FMA-UE classification defines levels of UE motor ability by describing UE movement tasks (FMA-UE items) which patients in each level can easily perform, cannot perform (too hard), and are well-matched to ability level. This information is the basis for designing task-practice sessions to specifically target the patient movement abilities. Because treatment is likely to induce changes in these variables, it is reasonable to expect changes in participants' Rasch FMA-UE measure.

Approach: *Dependent Variable:* The dependent variable will be change in UE motor impairment as measured by the percent change in the Rasch FMA-UE occurring from pre- to post-intervention. The Rasch FMA-UE percent change will be calculated as Post minus Pre divided by Pre.

Independent Variables: The independent variable is Group. The independent variable has two levels; targeted-therapy and non-targeted therapy.

Data Analysis: ANOVA will be used to compare the mean values of the Rasch FMA-UE change scores for each targeted vs. non-targeted treatment group across each impairment level (mild, moderate, severe). We will correct for multiple comparisons, therefore, significance for all comparisons will be alpha = 0.05/3 = 0.02.

Specific to Aim 2: Determine critical neuromechanical factors that influence response to targeted or *non*-targeted therapy

Hypothesis: Response to targeted therapy will be associated with recovery of "normal" UE movement and muscle activity patterns.

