**Medical University of South Carolina
Statistical Analysis Plan**

PI Name: [name], OTR/L

Study Title: Patient-Targeted Upper Extremity Rehabilitation After Stroke

Identifiers: NCT01819506 **Unique Protocol ID:** N0799-R

Version 4.0

Date: 08/01/2016

Statistical Analysis Plan

Aim 1: To test the effect of patient-specific targeted practice. Rationale: We hypothesize that task practice at the just-right challenge of difficulty will maximize post-stroke motor skill reacquisition. We expect that “targeted practice”, will increase UE motor ability because the difficulty of task goals will be matched and systematically progressed according to patients’ initial and evolving levels of ability. The Rasch UE motor ability measurement framework defines levels of UE motor ability by describing UE movement tasks (FMA-UE items) which patients in each level can easily perform, cannot perform (too hard), and are well-matched to ability level. This information is the basis for designing and progressing task-practice sessions to specifically target patient-specific movement abilities.

Approach: Dependent Variable: The dependent variable will be the Rasch FMA-UE person measure. Independent Variables: The independent variables are Group and Time. The between subjects factor “Treatment” has 2 levels (Targeted vs. Non-Targeted therapy) with 3 impairment levels nested within each level (mild, moderate, severe). The within subjects factor “Time” has 3 levels; Pre, Mid, Post. Data Analysis: A two-way mixed model ANOVA will be used to assess the main effect of Treatment. Significance for all comparisons will be alpha = 0.05. Covariate: intensity of training (averaged number of repetitions per session).

Missing Data: Since each patient will be observed over a 3-week period it is possible that the patient will miss a visit and/or drop out. If a patient misses a testing session, the session will be rescheduled to the next visit. If the patient drops out an intent-to-treat analysis will be applied and the missing data will be treated as missing at random (MAR). If missing occurs, multiple imputation methods will be used for data analysis (PROC MI and PROC MIANALYZE, in SAS version 9.3). This process will be overseen by the biostatistician [name].

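### The only stated power (90%, 18 per group, alpha 0.05) matches neither of the two conflicting Aim 1 analyses in the protocol and the SAP

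*Protocol*

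**What the plan says.** **Sizing (Protocol, section D, Study Design).** The null hypothesis is equality of the targeted and non-targeted means, two-tailed. The effect size comes from post-training Rasch person measures in the pilot: 2.30 (SD 1.00) against 1.42 (SD 0.45) logits, d = 1.13. The paragraph continues: "With an alpha level = 0.05, for a two-tailed hypothesis test at a 90% power level, the sample size calculation specified that 18 individuals"; this is the requirement for every group. Six groups give 108, raised to 130 for an expected 20% drop-out.

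**Protocol analysis (section D, Specific to Aim 1).** The outcome is percent change: "The Rasch FMA-UE percent change will be calculated as Post minus Pre divided by Pre". ANOVA compares mean change "for each targeted vs. non-targeted treatment group across each impairment level (mild, moderate, severe"), and "significance for all comparisons will be alpha = 0.05/3 = 0.02".

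**SAP analysis (Aim 1).** The SAP carries the same version number (4.0) and date (08/01/2016) as the protocol. It states: "The dependent variable will be the Rasch FMA-UE person measure". Time "has 3 levels; Pre, Mid, Post", with impairment level nested within treatment and training intensity as a covariate. On the test it says: "A two-way mixed model ANOVA will be used to assess the main effect of Treatment". On the error rate it says: "Significance for all comparisons will be alpha = 0.05".

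Neither document says which analysis is primary, and neither gives power for the analysis it describes.

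**The concern.** The sample size is built by multiplying a two-group calculation by six cells, so a reader will naturally take 90% as the power in each impairment level. The Aim 1 section then tests each level at a third of the alpha used for sizing, on a different variable. The SAP replaces those three tests with a single pooled test on another outcome at an uncorrected alpha.

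Two things are at stake. First, with two live rules, the Aim 1 conclusion can depend on which document is followed, and the choice could be made after the data are seen. Second, the one power figure given describes neither rule.

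**Working it through.** **1. Reproduce the stated figure.** Pooled SD = sqrt((1.00² + 0.45²)/2) = 0.775, and d = 0.88/0.775 = 1.135 (stated as 1.13). A two-sided two-sample t-test at 0.05 with d = 1.13 has non-central t power of 90.9% at 18 per group and 89.1% at 17. So 18 is correct for that test.

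**2. Protocol stratum tests: change only the alpha.** Inputs are d = 1.13 at face value, with equal strata and 1:1 allocation assumed, because Study Design gives no ratio or quotas. Non-centrality = d × sqrt(n/2), with n = N/6. In each cell the lower figure is separate t-tests (2n − 2 df) and the upper is error pooled over six groups (N − 6 df).

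| N analysed | n per group | alpha 0.05 | alpha 0.02 (printed) | alpha 0.0167 |
|---|---|---|---|---|
| 108 | 18 | 90.9–91.9% | 82.3–84.6% | 80.3–82.8% |
| 104 (130 × 0.8) | 17.3 | 89.7–90.9% | 80.5–83.0% | 78.4–81.2% |
| 130 (no loss) | 21.7 | 95.3–95.8% | 89.8–91.2% | 88.4–90.0% |

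The last row is a ceiling for what the SAP's multiple imputation could recover. If one stratum held only 25% of 104 (13 per arm, purely illustrative), power at 0.0167 would be 62–67%. Part of that fall is the imbalance itself: at 0.05 the separate t-test would already be at 79%.

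**3. Protocol outcome.** The figures in step 2 isolate the alpha mismatch. They are not power for percent change. Table 4 places the severe level below −0.22 logits, so Pre is negative there and every improvement gives a negative percent change. For illustration, moving from −1.0 to −0.5 gives 0.5/(−1.0) = −50%. The moderate level (−0.22 to 2.44) spans zero, where the ratio has no bound. A d computed on post-training logits says nothing about power for this variable.

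**4. SAP main effect.** This averages the arm difference over three visits. At Pre, randomised arms should not differ (pilot 0.90 against 0.89, section B, 2h). Let f be the share of the Post effect present at Mid, and r the within-person correlation, with equal SDs:

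effective d = 1.135 × (0 + f + 1)/3 ÷ sqrt((1 + 2r)/3), tested at 0.05 on N − 6 df.

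The documents give neither f nor r. With r from 1.0 (lower power) to 0.5 (higher power):

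| Effect at Mid | Effective d | Power, N = 104 | Power, N = 130 | Post d needed for 90%, N = 104 |
|---|---|---|---|---|
| none (f = 0) | 0.378–0.463 | 48–65% | 57–75% | 1.57–1.93 |
| half (f = 0.5) | 0.567–0.695 | 82–94% | 89–98% | 1.05–1.28 |
| full (f = 1) | 0.757–0.927 | 97–99.7% | 99% or more | 0.79–0.96 |

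The last column uses the effective d that gives 90% with 104 (0.642): Post d = 0.642 × 3/(1 + f) × sqrt((1 + 2r)/3). A simulation with N = 102, three strata and three visits (r = 0.99 / 0.5) agreed: 0.489/0.631, 0.815/0.929 and 0.970/0.998 for f = 0, 0.5 and 1.

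**5. Smaller slips.**
- 0.05/3 = 0.0167, not 0.02. Three independent tests at 0.02 give 1 − 0.98³ = 5.9% family-wise error (bound 3 × 0.02 = 6%).
- 108 × 1.2 = 129.6, which is the 130. Keeping 108 after 20% loss needs 108/0.8 = 135; 130 tolerates 1 − 108/130 = 16.9%.
- The Project Timeline enrols 20 + 48 + 40 = 108, while the text says 130.

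**The case against.** Several counter-arguments have some force.

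- **The SAP is closer to the sizing than to the protocol's analysis.** It shares alpha 0.05 and the logit scale with the sizing paragraph and differs from it only in the test. This stands. For the SAP the point is that 90% was never calculated for its test, not that power is shown to fall short.
- **The SAP range rests on assumed inputs.** It does, and it lies on both sides of 90%. A correlation of 1.0 is a limiting case; at r = 0.3 with no Mid effect and 104 completers, power is 74%. The training-intensity covariate is also left out. The range shows only that 90% does not carry over.
- **The hypothesis is stated as one pooled comparison.** A Post-only comparison of 54 against 54 with d = 1.13 in every stratum has power above 99.9%. That is true, but neither document specifies this test.
- **The printed alpha is 0.02.** At that value the loss is smaller (82–85% with 108), and with no drop-out power returns to about 90–91%. Both alphas are shown above, and the plan itself expects 20% loss.
- **The Data Analysis text says change scores.** The only change variable defined in that section is the percent change just above it.
- **The timeline total may reflect a table damaged in extraction.** That is possible, and it is treated as minor.

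None of this removes the conflict between the two Aim 1 rules.

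**Conclusion.** The concern holds and must be fixed. The sizing arithmetic is right for the test it describes, but that test is in neither Aim 1 analysis, and the two analyses disagree on outcome, test and alpha with no rule for which prevails.

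For the protocol's stratum tests, the alpha mismatch costs about 6 to 11 points at 18 per group, and with the stated drop-out power is about 78–83% across both alphas. These figures assume d = 1.13 in every stratum, equal strata and 1:1 allocation, and they do not describe percent change. For the SAP test no single figure can be derived. The assumption about d is itself weak, because it comes from post-training scores in 12 people with moderate impairment. Confidence in the mismatch is high because it is visible in the text.

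**What to change.** State in both documents one primary outcome variable, one primary test and one alpha rule. Two coherent choices are:

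1. A pooled comparison stratified by impairment level at 0.05 that targets the Pre-to-Post difference, for example the Post person measure adjusted for Pre, or the Treatment-by-Time contrast. The stratum results become secondary.
2. Three stratum tests at 0.0167 each, or with Holm's procedure.

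Recalculate power for the chosen test on the chosen outcome, with stated stratum sizes, allocation and drop-out, and say that d comes from post-training scores in a 12-person pilot with moderate impairment. If the stratum rule is kept, withdraw the 90% figure, and quote 78–83% only as the consequence of the alpha mismatch and drop-out at d = 1.13.

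In the same edit, write 0.0167 for 0.02, give the tolerated drop-out as about 17%, and reconcile the timeline total of 108 with 130.

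The cost is text changes in both documents and one power calculation. No extra enrolment is asked for.

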Identifying and describing those that respond and do not respond to rehabilitation treatment is a growing area of interest in rehabilitation science. Here we aim to differentiate patterns of recovery in our sample by integrating Growth Mixture Modeling (GMM) into our Rasch FMA-UE measurement framework. This is a highly novel method for defining responders and non-responders. Although well established in educational and psychological literature, GMM is a new to rehabilitation science and has been used in only a few stroke rehabilitation studies to date.^{55,58,59}

GMM offers a robust method of identifying subgroups of people with stroke who follow distinct trajectories of UE recovery. In contrast to analyses that focus on mean-level change in a sample, GMM elucidates how different people recover in different ways. GMM separates repeated measurements of a sample into groups of individuals showing similar patterns of change over time. In addition, the analysis specifies factors predicting these distinct patterns. When placed into the Rasch FMA-UE measurement framework, the results of the GMM analysis will

enable a clear description of each subgroup because the subgroup's pattern of UE recovery will be directly connected to a description of the specific FMA-UE items that can/cannot be performed.

2h. Pilot study: targeted-rehabilitation versus non-targeted rehabilitation

Our recent pilot work³² provides evidence that a targeted rehabilitation intervention maximizes UE motor function when compared to non-targeted intervention. We conducted a pilot study (n=12, with 6 subjects per intervention group) which investigated the effects of an intervention targeted at participants with moderate post-stroke UE motor impairment, specifically those individuals who displayed reduced shoulder-elbow interjoint coordination and excessive anterior trunk flexion. The intervention was "targeted" meaning that it afforded opportunity for participants to practice a more normal reaching pattern characterized by concurrent shoulder

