Figure 5 presents elbow AROM (y-axis) averaged for each FMA-UE impairment category (x-axis). Elbow AROM is shown as a percentage of normal range of motion. As expected, and consistent with Figure 4 above, those with severe UE impairment exhibited the lowest elbow AROM and those with mild impairment exhibited more normal elbow AROM. Post-hoc pairwise comparisons were all statistically significantly different (all comparisons $p<0.05$).

Figure 4 presents angle-angle plots. Panels A-C in red present kinematic data from 3 representative individuals with stroke. The rightmost panel in blue presents kinematic data from a neurologically healthy individual. Elbow extension (x-axis) is plotted with shoulder flexion (y-axis) for the 4 individuals. Person A (left panel) has severe UE motor impairment as evidenced by

[figure not shown]

Figure 6: Hand Path Curvature

[figure not shown]

Figure 7: Muscle onset

3f. Pilot tested targeted vs. non-targeted rehabilitation for one UE impairment category

In published research³² we conducted a pilot study to establish feasibility of our patient-targeted UE rehabilitation approach. We enrolled 12 individuals with stroke, 6 to each of two UE rehabilitation interventions. One intervention was targeted at the movement deficits of people with moderate stroke, the other intervention did not specifically target movement deficits but instead promoted overall arm-use.

We first utilized the Rasch FMA-UE to describe specific motor abilities of the sample and documented that individuals with moderate UE motor impairment fluctuate between partial ability and near normal ability to perform movements requiring simultaneous control of two joints. For this group of individuals, a key motor behavior marking an expected next step in the recovery process is the ability to simultaneously control two joints while moving a third. Therefore, we designed an intervention to match the ability level of this category.

The targeted-training group performed all task-practice sessions behind a trunk restraint that prevented anterior trunk motion (see photo to left). Tasks for this group were located to afford repeated use of a shoulder flexion-elbow extension reaching pattern. The non-targeted treatment, constraint induced movement therapy delivered in its signature dose, was intended to provide high-dose repetitive task practice but was not aimed at altering any specific movement pattern.

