Dose: All subjects in all groups will engage in 12 rehabilitation sessions (3x/week over 4 weeks).. Recent data suggest that the dose of practice, e.g., number of movement repetitions, is important to produce neural reorganization and motor learning.⁷¹ We therefore will provide approximately 200 reach-to-grasp/touch repetitions per session which previous research has shown to be safe for people with stroke and feasible to accomplish in 2-

3 hours.⁷² **Treatment Groups:** Targeted practice is defined as an evidence-based intervention targeted to specific UE motor deficits characteristic of persons in each UE impairment level. Non-targeted task practice is defined as a “standard of care” intervention that consists of task practice with no guidance from measurement to choose appropriate tasks to address specific underlying deficits. **Table 4** presents a summary of the treatments.

Table 4: Summary of treatments

Rasch FMA-UE Impairment Level	Rasch FMA-UE Person Measure	Targeted Treatment	Non-Targeted Treatment
Mild	>2.44 logits	Forced-use task practice	Functional Upper Extremity Training
Moderate	- 0.22 to 2.44 logits	Task practice with trunk restraint	
Severe	<-0.22 logits	Task practice with trunk restraint and faded arm support	

Targeted Practice Treatment: A person with mild UE motor impairment has a 50% probability of accomplishing FMA-UE items requiring fine motor coordination and dexterity, i.e., items well-matched to his/her ability described in Table1. For people with this level of UE motor impairment *Forced use task practice* is an optimal evidence-based intervention.⁷³ Forced use therapy, like Constraint-Induced Movement Therapy²⁸ although not delivered in its “signature” dose, restrains participants’ less affected UE in a glove to prevent its use thereby “forcing” exclusive use of the affected UE. The premise of the strategy is that repetitive object grasp, manipulation reduces “learned non-use”.⁷⁴ The intervention is shown to improve fine motor dexterity, movement speed, and smoothness.^{31,32}

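### The 18-per-group sample size applies one effect size from a 12-person, moderate-only pilot to six groups with other therapies and another comparator, and the 90% power does not hold at the protocol's by-level alpha

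*Protocol*

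**What the plan says.** The sample-size paragraph in Protocol section D takes the pilot's post-treatment results. The trunk-restraint group "exhibited a post-training Rasch-derived FMA-UE person ability measure of 2.30 (± 1.00) logits" and the control group "exhibited a post-training Rasch FMA-UE score of 1.42 (± 0.45) logits", "which yields a Cohen's d effect size of 1.13". With alpha set at 0.05, it then states that "for a two-tailed hypothesis test at a 90% power level, the sample size calculation specified that 18 individuals are needed in each group". Six groups give N = 108. The hypothesis written there is the overall one, targeted against non-targeted.

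Section 2h describes the pilot as 12 people, 6 per arm, with moderate impairment, "specifically those individuals who displayed reduced shoulder-elbow interjoint coordination and excessive anterior trunk flexion". The heading of section 3f says it covered one impairment category. The comparator was constraint-induced therapy: "The non-targeted treatment, constraint induced movement therapy delivered in its signature dose". Therapy time was 4 hours a day over 10 days.

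The trial enrols mild, moderate and severe patients for twelve 2-hour sessions. In Table 4 the targeted therapy is trunk restraint at the moderate level, trunk restraint with faded arm support at the severe level, and forced use at the mild level. The protocol describes the last as "Forced use therapy, like Constraint-Induced Movement Therapy", though not at the same dose. The comparator at all three levels is Functional Upper Extremity Training.

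Two analyses are planned. The protocol (Specific to Aim 1, Data Analysis) compares the arms within each impairment level at 0.05/3. The SAP tests the main effect of treatment, with impairment level nested, at 0.05.

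**The concern.** A power statement is only as good as the effect it assumes. Here one observed d, from one severity category and one pair of therapies, sizes three comparisons. Two of them concern patients the pilot did not study, and none uses the pilot's comparator. The protocol offers no argument for carrying d across.

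The trial's premise is that treatment should be matched to impairment level, so the by-level results will be read. If a mild or severe comparison is non-significant and the reader takes the design to have 90% power there, the result will look like evidence of no effect when it may only be imprecise. The stated 90% is also computed at alpha 0.05, not at the alpha the protocol sets for the by-level comparisons.

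**Working it through.** **1. Reproduce the protocol's figure.** Inputs from the sample-size paragraph: means 2.30 and 1.42, SDs 1.00 and 0.45, two-sided alpha 0.05, power 90%.

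- Pooled SD = sqrt((1.00² + 0.45²)/2) = 0.775.
- d = (2.30 - 1.42)/0.775 = 0.88/0.775 = 1.13.
- Power is from the noncentral t with df = 2n - 2 and noncentrality d × sqrt(n/2). At d = 1.13, n = 17 gives 0.891 and n = 18 gives 0.909.

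So 18 per group is correct for these inputs, and 18 × 6 = 108. The arithmetic is sound. The question is where d comes from and which test it is applied to.

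**2. Precision of the pilot d.** With 6 per arm, t = 1.135 × sqrt(6/2) = 1.97 on 10 df, p = 0.078. Inverting the noncentral t gives a 95% CI for d of about -0.12 to 2.34.

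**3. Does the pilot contrast match the trial's?**

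| | Pilot | Trial, mild | Trial, moderate | Trial, severe |
|---|---|---|---|---|
| Targeted therapy | trunk restraint | forced use | trunk restraint | trunk restraint + faded arm support |
| Comparator | constraint-induced therapy | Functional Upper Extremity Training | same | same |
| Therapy time | 4 h × 10 = 40 h | 2 h × 12 = 24 h | same | same |
| In pilot population? | n/a | no | yes | no |

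The moderate level matches on severity and targeted therapy, but not on comparator or time. The mild level matches on no row, and the severe level only in that its therapy includes trunk restraint.

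**4. Power of the planned tests.** By level: 18 v 18, noncentrality d × sqrt(18/2) = 3d, df 34, alpha 0.05/3 = 0.0167. Pooled: 54 v 54, noncentrality d × sqrt(54/2) = 5.196d, df 106, alpha 0.05. The pooled column is a simple two-sample approximation to the SAP's mixed model, with d the average effect over the three levels.

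| d (assumed) | By level, alpha 0.05/3 | By level, alpha 0.05 | Pooled 54 v 54, alpha 0.05 |
|---|---|---|---|
| 1.13 | 80% | 91% | >99% |
| 0.8 | 46% | 65% | 98.5% |
| 0.6 | 25% | 42% | 87% |
| 0.5 | 17% | 31% | 73% |

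- The effect with 90% power by level at 0.05/3 is d = 1.28. At alpha 0.05 it is 1.11.
- If d = 1.13 does hold, 90% power by level at 0.05/3 would take 23 per group.
- The protocol prints 0.05/3 as 0.02. At 0.02, power at d = 1.13 is 82%, so the rounding matters little.
- The pooled test has 90% power at an average d of 0.63.
- If only the moderate level has the pilot effect, the average is 1.135/3 = 0.38 and pooled power is about 50%. If only the mild level has no effect, the average is 2 × 1.135/3 = 0.76 and pooled power is about 97%.

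**The case against.** The strongest reply is that the protocol never claims 90% power at each level. Its written hypothesis is the overall contrast, and the SAP tests a pooled treatment effect, for which 54 v 54 is far more generous. This is right as far as it goes. A reader might infer a per-level guarantee from the paragraph, but the text does not state one. Nor do the documents show that the trial as a whole is too small: on the pooled approximation an average d of 0.63 suffices for 90% power. What stands is that 18 v 18 is the comparison actually sized, the protocol's Aim 1 analysis makes that comparison three times at a stricter alpha, and the pooled test also depends on mild and severe effects the pilot did not measure.

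Three other strong readings go further than the documents allow.

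- One might say that d = 1.13 and 90% are valid for the moderate level alone. They are not established there either: comparator and therapy time differ from the pilot's, and at 0.05/3 the power is 80%.
- One might conclude that the mild level's targeted therapy is weak because it resembles the pilot's control. The protocol says the dose differs, the pilot control group itself rose from 0.89 to 1.42 logits, and forced use is tested here against another programme. The true effect could be smaller or larger than 1.13.
- One might treat the reaching deficit as an extra entry filter in the pilot. The wording may only describe what moderate patients typically show, since section 3f gives two-joint difficulty as a feature of that category. The point does not depend on it.

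It is also fair that the protocol discloses the source of d openly, and that the severe level's therapy contains the pilot's trunk restraint.

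**Conclusion.** The point holds in this form: the sample size rests on a single imprecise effect from a moderate-only pilot with a different comparator and therapy time, and nothing in the documents justifies using it at the mild or severe level or against the trial's comparator. The 18 per group reproduces. The 90% does not carry over to the protocol's by-level tests, where power is 80% even if d = 1.13 is true and falls to 46% at 0.8 and 17% at 0.5.

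This rests on three assumptions. The smaller effects are illustrative, because the documents give none for mild or severe patients. The calculations take 18 analysed patients per arm in every level. And d is treated as the standardised difference on whatever scale is analysed, although the pilot d is on post-treatment logits and the protocol's Aim 1 outcome is percent change. The pooled figures also ignore the SAP's repeated measures and covariate.

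The consequence is for what a non-significant by-level result can be taken to mean. It is not a case for a different N.

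**What to change.** Revise the sample-size paragraph in Protocol section D, leaving N unchanged:

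1. State that d = 1.13 comes from a moderate-only pilot of 12 people with a different comparator, and is an assumption at all three impairment levels.
2. For the by-level tests, replace the 90% figure with power at 18 v 18 and alpha 0.05/3: 80% at d = 1.13, 46% at 0.8, 25% at 0.6, 17% at 0.5, and 90% only at d of about 1.28.
3. Give separately the power of the SAP's pooled treatment test (54 v 54, alpha 0.05, simple two-sample approximation): 73% at an average d of 0.5, 90% at 0.63, and about 50% if only the moderate level has the pilot effect.
4. State that a non-significant result within an impairment level will be reported with its confidence interval as inconclusive, not as evidence of no effect.

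The cost is one rewritten paragraph and a less favourable stated power. Enrolment, treatment and the planned tests are untouched.
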